IRB	Institutional Review Board
VAS	Visual Analog Scale

Study Summary

Title	Diagnosis and monitoring of eosinophilic esophagitis using the Cytosponge
Methodology	This will be a prospective cohort study, with patient enrollment conducted at UNC and Mayo Clinic by Drs. [name] and [name], and further sample analysis performed by [name]. In Aim 1, patients with eosinophilic esophagitis (EoE) or suspected EoE will be enrolled, tissue will be obtained from both the Cytosponge and routine care endoscopy, and the methods will be compared for a single time point to determine accuracy of Cytosponge for quantifying esophageal eosinophil counts. The patients who are being treated will be followed and tissue will be assessed over time with both Cytosponge and routine care endoscopy to determine the utility of Cytosponge for monitoring treatment response in patients with EoE. For all patients, safety will be monitored and subjects will complete a survey about the acceptability of Cytosponge (Aim 2).
Study Duration	2 Years
Study Center(s)	University of North Carolina, Chapel Hill, NC Mayo Clinic, Rochester MN
Objectives	
Aim 1: To determine the accuracy of Cytosponge for quantifying esophageal eosinophil counts in patients with active EoE, as compared to endoscopy with biopsy as the gold standard.
 
Aim 2: To determine the safety and acceptability of Cytosponge for patients with EoE.

Number of Subjects	150

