1.2 Background

Eosinophilic esophagitis (EoE) is an emerging disease defined by the abnormal presence of eosinophils in the esophageal lining, leading to trouble swallowing (dysphagia), esophageal narrowing (stenosis), and food impaction.¹⁻³ The incidence and prevalence of EoE have risen dramatically,⁴⁻⁷ and EoE is now the most common cause of food impaction in patients presenting to emergency rooms.^{8, 9} In order to diagnose and monitor EoE, upper endoscopy with esophageal tissue biopsy is currently required. Two upper endoscopies are needed to diagnose EoE, the first one to evaluate symptoms and the second one to confirm the diagnosis after treatment with a proton pump inhibitor (anti-acid) medication.³ If a patient is treated with a swallowed ("topical") steroid medication such as budesonide or fluticasone, they undergo a third endoscopy to determine whether the medication was effective.¹⁰⁻¹⁴ If they are treated with an

elimination diet, they will require an endoscopy 6 weeks after the initial elimination, and then another one every 4-6 weeks after each food is added back.¹⁵⁻¹⁷ In some cases this can add up to more than 8-10 endoscopies in a single year. This is costly, inconvenient, and the repeated procedures add risk. New diagnostic methods for EoE are urgently needed.

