- Have a history of esophageal stricture that precludes passage of an adult endoscope,
- Have any history of esophageal varices, liver impairment of moderate or worse severity (Child's-Pugh class B & C), or evidence of varices noted on any past endoscopy,
- Have any history of esophageal surgery (except uncomplicated fundoplication), and history of coagulopathy, with INR >1.3 and/or platelet count of <75,000.

Cytosponge administration will occur after an overnight fast to minimize the possibility of aspiration of any gastric contents. Every administered sponge will be assessed post-procedure for signs of fracture or incomplete retrieval of the sponge. In the unlikely case of incomplete retrieval, the sponge will be retrieved with a Roth net at the standard of care endoscopy which will routinely immediately follow the administration of the sponge per the study protocol. Any bleeding noted, either clinically following the sponge administration or due to blood on the sponge itself, will be similarly investigated, and, as necessary, treated during the subsequent endoscopy. Because study inclusion/exclusion criteria are designed to exclude those at highest risk for a bleeding complication, the risk of bleeding in this study should be extremely low.

2 Study Objectives

Aim 1: To determine the accuracy of Cytosponge for quantifying esophageal eosinophil counts in patients with active EoE, as compared to endoscopy with biopsy as the gold standard.

Aim 2: To determine the safety and acceptability of Cytosponge for patients with EoE, all patients who are enrolled in both Aims 1 and 2 will be monitored.

3 Study Design

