3.1 General Design

This is a prospective longitudinal cohort study, with patient enrollment conducted at UNC and Mayo Clinic by Drs. [name] and [name], and further sample analysis performed by [name]. In Aim 1, patients with EoE will be enrolled, tissue will be obtained from both the Cytosponge and endoscopy, and the methods will be compared for a single time point. For all patients, safety will be monitored and subjects will complete a survey about the acceptability of Cytosponge (Aim 2).

Subject recruitment will be from consecutive eligible patients presenting for endoscopy as part of their routine care. Potentially eligible subjects will be contacted by telephone in advance of their procedure and their interest in study participation assessed. Subjects interested in participating will be asked to present to the endoscopy unit prior to their scheduled procedure. At that time, inclusion and exclusion criteria will be reviewed, and eligible subjects will give informed consent. Subjects will then undergo the Cytosponge assay.

After the Cytosponge has been removed, the patient will undergo standard upper endoscopy and biopsy, as clinically indicated. During this exam, endoscopic features of EoE will be recorded, including rings, furrows, white plaques, decreased vascularity, and strictures. The severity of the endoscopy findings will be measured using the recently validated EREFS scoring system.²³ Four esophageal biopsies will be taken both from the distal (5 cm above the gastro-esophageal junction) and proximal (15 cm above the gastro-esophageal junction) esophagus. This number of biopsies has been shown to maximize the diagnostic sensitivity for EoE.²⁴

Enrolled subjects will be administered the Cytosponge during the enrollment visit. After enrollment, if subjects receive treatment for their EoE and return to the enrolling site for an upper endoscopy as part of their standard of care, then subjects will be asked to repeat the Cytosponge procedure prior to each follow-up standard of care endoscopy.

Histology and eosinophil counts

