3.2 Protocol Map

3.3 Primary Outcomes

The primary outcome variables will be sensitivity and specificity of the cytosponge, as compared against the gold standard of the presence of EoE as detected by upper endoscopy with biopsies.

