4.1 Inclusion Criteria

1. Able to read, comprehend, and complete the informed consent form
2. Male or female subjects, age 18-80 years,
3. Suspected EoE or has a diagnosis of EoE with current active disease,

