6.2 Statistical Methods

Aim 1: To test the hypothesis that the Cytosponge accurately quantifies esophageal eosinophil counts in patients with active EoE, the maximum eosinophil counts from the Cytosponge and endoscopic biopsy will be compared by calculating the Pearson coefficient of correlation. In addition, patients will be categorized as having an eosinophil count either above or below 15 eos/hpf (the current diagnostic threshold). Agreement between patients above and below this threshold for Cytosponge and endoscopic biopsy will be measured using the kappa statistic. If eosinophil counts are not normally distributed, non-parametric methods will be used. Separate analyses will be performed for patients with active EoE and patients undergoing treatment.

Aim 2: Summary statistics will be calculated to describe adverse events and the tolerability of the Cytosponge. The proportion of subjects who prefer the Cytosponge will be calculated.

We predict that the Cytosponge will be safe and well-tolerated in patients with EoE, and that they will prefer this minimally invasive method to endoscopy with biopsy. We also predict that the eosinophil counts obtained with Cytosponge will strongly correlate with the counts from endoscopy with biopsy in both patients with active EoE.

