6.3 Subject Population for Analysis

The population whose data will be subjected to the study analysis will include all subjects enrolled in this study that completed the Cytosponge administration and have pathology results available from the subsequent routine care endoscopy with biopsy.

7 Safety and Adverse Events

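### Do the two analysis groups in Section 6.2 leave out suspected-EoE subjects with a negative biopsy, and so undermine kappa and specificity?

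*Combined protocol and SAP*

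**What the plan says.** The Aim 1 population is worded in three ways.

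- Study Summary, Methodology: "In Aim 1, patients with eosinophilic esophagitis (EoE) or suspected EoE will be enrolled".
- Section 3.1: "In Aim 1, patients with EoE will be enrolled".
- Section 2, and the hypothesis in Section 6.2: active EoE. Section 2 gives the aim as "quantifying esophageal eosinophil counts in patients with active EoE, as compared to endoscopy with biopsy as the gold standard".

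Entry under Section 4.1 is by "Suspected EoE or has a diagnosis of EoE with current active disease". The primary outcome in Section 3.3 is "sensitivity and specificity of the cytosponge, as compared against the gold standard of the presence of EoE as detected by upper endoscopy with biopsies". Kappa, a secondary outcome in Section 3.4, is described in Section 6.2 for subjects split at 15 eos/hpf.

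Section 6.2 then adds: "Separate analyses will be performed for patients with active EoE and patients undergoing treatment". Section 6.3 defines the analysis population as "all subjects enrolled in this study that completed the Cytosponge administration" and who also have pathology from the endoscopy that follows.

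**The concern.** Section 4.1 lists suspected EoE and known active EoE as alternatives, so a suspected subject is not obviously active at entry. Section 1.2 states: "In order to diagnose and monitor EoE, upper endoscopy with esophageal tissue biopsy is currently required". On that footing a suspected subject could become active only through the study biopsy, which is also the reference standard. A suspected, untreated subject with a negative biopsy therefore has no place in either group that Section 6.2 names.

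These subjects matter. Section 4.1 does not admit patients in remission, who gave the pilot in Section 1.3 its range of severity, so suspected subjects are the natural source of negatives at the enrollment visit. If kappa and specificity were taken only within an active group, most negatives could be lost. If the study biopsy decided who counted as active, the reference standard would remove its own negatives. The 60 subjects that Section 6.1 assigns to Aim 1 would be equally unclear.

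**Working it through.** **The plan's own figures.** Section 6.1 gives n = 60, R = 0.40, alpha 0.05 and power 0.9. By Fisher's z, two-sided, power = Φ(atanh(0.40) × √57 − 1.96) = Φ(3.20 − 1.96) = 0.892, which agrees. The kappa power of 0.8 (0.7 against 0.4) depends on marginal shares that are not stated. With 50% biopsy-positive and 65% Cytosponge-positive, the large-sample two-sided calculation gives 0.815. Neither figure is disputed.

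**What the restricted reading would cost.** The pilot accuracy in Section 1.3 is sensitivity 100% and specificity 70%. Three further inputs are assumptions, not in the documents: suspected share s = 0.5; biopsy-positive share among suspected subjects ps = 0.5; biopsy-positive share among known-active subjects pa = 0.9.

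Negatives among 60 enrollment pairs:

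- pooled: 60[s(1 − ps) + (1 − s)(1 − pa)] = 60(0.25 + 0.05) = 18
- active group: 60(1 − s)(1 − pa) = 3
- in neither group: 60s(1 − ps) = 15

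Kappa ranges below are the 2.5th to 97.5th percentiles of 200,000 multinomial draws, counting undefined kappa as 0. With sensitivity 100%, kappa is 0 or undefined exactly when no true negative is seen, so its probability is (1 − 0.7q)^n, where q is the biopsy-negative share. Specificity intervals are exact (Clopper-Pearson).

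| Set | n | Negatives | Kappa range | P(kappa 0 or undefined) | Specificity (95% CI) |
|---|---|---|---|---|---|
| Section 6.3, pooled | 60 | 18 | 0.56 to 0.93 | below 0.0001 | 13/18 (0.47 to 0.90) |
| Active by entry label | 30 | 3 | 0 to 1 | 0.93^30 = 0.113 | 2/3 (0.09 to 0.99) |
| Entry label plus suspected with a positive biopsy | 45 | 3 | 0 to 1 | 0.953^45 = 0.116 | 2/3 (0.09 to 0.99) |
| Active by entry label, 150 enrolled | 75 | 7.5 | 0.48 to 1.00 | 0.93^75 = 0.004 | not computed |

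Median kappa at 60 enrolled is 0.76 pooled and 0.78 in the entry-label active group, so the loss is of precision, with little shift in the typical value.

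Over s = 0.25 to 0.75, ps = 0.3 to 0.7 and pa = 0.8 to 1.0, between 33% and 100% of the negatives fall in neither group. That leaves 0 to 9 in the active group against 4.5 to 34.5 pooled. At the mildest corner (0.25, 0.7, 0.8) kappa ranges over 0.48 to 1.00 in the active group and 0.53 to 0.95 pooled.

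**Whether the plan calls for the restricted reading.**

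1. Section 6.3 is the only section that defines who is analysed. A suspected subject with a completed sponge and a negative biopsy is included.
2. In Section 6.2, active EoE appears in the hypothesis and in the sentence on separate analyses. The kappa sentences refer simply to patients.
3. Section 6.2 contains no sensitivity or specificity analysis, so it cannot confine specificity to a group. Section 3.3 defines specificity against biopsy without limiting the population.
4. No sentence says that the separate analyses replace the Section 6.3 analysis.
5. The contrast between active and treated follows the design: one pair at enrollment, then repeat pairs only after treatment (Sections 3.1 and 5.3). Read as enrollment against on-treatment, every first pair has a place.
6. The Study Summary and Section 3.1 say who is enrolled, while Section 2 names the target condition. Section 4.1 governs entry and agrees with the Study Summary; Section 3.1 is a shortened form.

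**The case for a change.** The best case for acting is that the ambiguity is real and cheap to remove. The plan nowhere links kappa, sensitivity or specificity to the Section 6.3 set by name, and Section 6.2 frames its hypothesis in active EoE. The version of the methods in the Study Summary omits the sentence on separate analyses, and the last sentence of Section 6.2 is visibly unfinished. An analyst could defend either population after seeing the data, and the primary outcome's denominator would change.

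What stands is that the wording varies and that Section 6.2 does not place the untreated, suspected, biopsy-negative subject. What does not stand is that this produces a wrong result. Choosing the narrow set means reading a sentence about separate analyses as overriding the section that defines the analysis population. It also means attaching specificity to a section that never mentions it. The case in which the active group has no negatives at all requires redefining active disease by the study biopsy for everyone, whereas Section 4.1 makes it an entry condition.

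The lack of a stated analysis of sensitivity and specificity in Section 6.2 is a separate matter and is not settled here.

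**Conclusion.** This is an ambiguity, and it needs no change. An analyst who follows Section 6.3 at the single time point given in the Study Summary and Section 3.1 obtains sensitivity, specificity and kappa with the biopsy-negative subjects included. The active and on-treatment analyses then sit beside that as subgroup results. Amending the text would mostly record the set that the plan already defines.

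The cost of the other reading could be large at 60 subjects: 15 of 18 negatives unplaced and about an 11% chance of a zero or undefined kappa. Those sizes rest on three shares that the documents do not give. They shrink to a 0.4% chance at the permitted 150 under the same assumptions, and at 60 the difference is small at the mildest corner of the range. The conclusion rests on taking Section 6.3 at its word, and no passage contradicts it.

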5.3 Follow-Up Cytosponge Administration

After enrollment, if subjects receive treatment for their EoE and return to the enrolling site for an upper endoscopy as part of their standard of care, then subjects will be asked to repeat the Cytosponge procedure prior to each follow-up standard of care endoscopy.

Patients will be followed and tissue will be assessed over time with both Cytosponge and routine care endoscopy; samples will be taken at up to 6 time points.

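### Section 6.2 does not say how up to six Cytosponge–biopsy pairs from one treated patient enter the treated-patient analysis; if they are pooled, the usual intervals would be too narrow

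*Combined protocol and SAP*

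**What the plan says.** - **Collection.** Under section 5.3, a subject who is treated and comes back for routine endoscopy gives a new pair each time: "subjects will be asked to repeat the Cytosponge procedure prior to each follow-up standard of care endoscopy". The ceiling is stated as "samples will be taken at up to 6 time points". Whether enrollment counts as one of the six is not said.
- **Purpose.** The Study Summary (Methodology) says that treated patients are followed with both methods "to determine the utility of Cytosponge for monitoring treatment response in patients with EoE".
- **Aim 1.** Section 3.1 says that "the methods will be compared for a single time point".
- **Analysis.** In section 6.2, maximum counts are "compared by calculating the Pearson coefficient of correlation", with non-parametric methods if the counts are not normal. For the 15 eos/hpf cut-off, "Agreement between patients above and below this threshold for Cytosponge and endoscopic biopsy will be measured using the kappa statistic". The same paragraph adds: "Separate analyses will be performed for patients with active EoE and patients undergoing treatment".
- **Population.** Section 6.3 "will include all subjects enrolled in this study that completed the Cytosponge administration" and have biopsy results from the endoscopy that followed. It is defined by subject and gives no rule for visits or pairs.

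The plan contains no rule for choosing a pair, no mixed model, no clustered or resampled variance, and no repeated-measures form of correlation or kappa.

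**The concern.** Inclusion (section 4.1) is by suspected EoE or a diagnosis with active disease, so the documented source of on-treatment pairs is follow-up, where one person can supply several. The usual standard errors of Pearson, rank correlation and kappa treat each pair as a different patient. Applied to pooled follow-up pairs, they would claim more information than the patients supply.

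Pooling would also change what is estimated. Section 1.2 describes one further endoscopy to judge a topical steroid, but with an elimination diet one endoscopy after the initial elimination and another after each food is added back. A pooled estimate would lean towards patients who have many endoscopies. At stake is the reliability of the evidence on monitoring, which the Study Summary names as a purpose of follow-up.

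**Working it through.** **1. The plan's own figure.** Section 6.1 gives N = 60, R = 0.40, power 0.9 and alpha 0.05. By Fisher's z, two-sided:

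power = Φ(atanh(0.40) × √(60 − 3) − 1.96) = Φ(0.4236 × 7.550 − 1.96) = Φ(1.238) = 0.892.

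This reproduces the stated 0.9. The calculation counts one pair per subject, so repeated pairs do not affect it. No sample size, power or interval is stated for the treated analysis, so there is no figure there to reproduce.

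**2. Inputs that must be assumed.** The documents give neither the pairs per treated patient (m) nor the share of variance between patients (ICC). I use m = 2, 3 and 5, where 5 is the maximum number of follow-up pairs if enrollment is one of the six time points. ICC is 0.3, 0.5 and 0.7.

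**3. Equal correlation between and within patients.** The variance of Fisher's z is inflated by about 1 + (m − 1) × ICC². For m = 5 and ICC = 0.5 this is 1 + 4 × 0.25 = 2.0, so the standard error is √2.0 = 1.41 times the naive one. The table compares this with a simulation of 60 pooled pairs, true correlation 0.7, 20,000 runs.

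| Patients × pairs | ICC | √(1 + (m − 1) × ICC²) | Simulated SE ratio | Coverage of nominal 95% interval |
|---|---|---|---|---|
| 30 × 2 | 0.3 / 0.5 / 0.7 | 1.04 / 1.12 / 1.22 | 1.05 / 1.12 / 1.23 | 94 / 92 / 89% |
| 20 × 3 | 0.3 / 0.5 / 0.7 | 1.09 / 1.22 / 1.41 | 1.08 / 1.22 / 1.43 | 93 / 89 / 83% |
| 12 × 5 | 0.3 / 0.5 / 0.7 | 1.17 / 1.41 / 1.72 | 1.15 / 1.39 / 1.73 | 91 / 84 / 74% |

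At ICC = 0 the ratio is 1.0 and coverage is 95%.

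**4. Weaker correlation within patients.** With 30 patients, a correlation of 0.7 between patients and 0.4 between visits, and ICC from 0.3 to 0.7:

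- 2 pairs each: SE ratio about 1.04 to 1.19, coverage about 93% to 90%.
- 5 pairs each: SE ratio about 1.15 to 1.64, coverage about 92% to 77%.

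As a check, coverage is close to 2Φ(1.96 / ratio) − 1. A ratio of 1.64 gives 2Φ(1.195) − 1 = 77%, and 1.19 gives 90%. A ratio of 1.04 gives 94% and 1.15 gives 91%, each within a point of the simulated value.

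**5. Uneven follow-up.** Suppose 20 patients give 1 pair, 6 give 2 and 4 give 5: 20 + 12 + 20 = 52 pairs. Four of 30 patients (13%) then supply 20 of 52 pairs (38%). At ICC 0.5 to 0.7 the SE ratio is about 1.14 to 1.28 and coverage about 91% to 87%.

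**6. Kappa.** In the settings of step 3, the SE ratio runs from 1.02 to 1.31 and coverage from 94% to 86%.

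**The case against.** The strongest reply is that pooling is nowhere in the plan. Section 3.1 speaks of a single time point, section 6.2 categorises patients, section 6.1 counts subjects, and section 6.3 defines its population by subject. The sentence on separate analyses sits in the Aim 1 paragraph. One pair per patient is a natural reading, and then there is no clustering. This stands, and it is why the point is conditional. It does not close the gap: on that reading the plan still does not say which of several follow-up pairs is used, and the choice could be made after the data are seen.

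A reader might infer more than the documents support:

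- **That the treated analysis must consist of several follow-up pairs per patient.** Sections 4.1 and 4.2 do not exclude someone with active disease who is already on treatment, so a treated pair could come from enrollment.
- **That a stated precision is wrong.** No interval, test or power is given for the treated group. The correlation and kappa as descriptive values do not need independent pairs; their usual standard errors do.
- **That the active and treated groups are compared as if independent.** Section 6.2 plans separate analyses and no test between them.
- **That the five-pair figures are the expected effect.** They are near the ceiling. Follow-up pairs arise only when a treated patient returns for routine endoscopy, and the Summary of Changes says that device availability limited the study's scope.

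The reach is also limited: section 6.2 describes no treated-group version of the primary outcomes, sensitivity and specificity.

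**Conclusion.** The point holds in conditional form. The plan collects repeated pairs from treated patients to judge monitoring and keeps a separate treated analysis, but names only methods whose usual standard errors assume one pair per patient. If follow-up pairs are pooled, the correlation interval is slightly to moderately too narrow with 2 pairs per patient and can be seriously too narrow with 5. All of this rests on the assumed between-patient share, number of pairs and correlations. The plan does not establish that precision will in fact be overstated. This is an inexpensive improvement to an unpowered analysis and does not threaten the powered Aim 1 comparison.

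**What to change.** In sections 6.2 and 6.3:

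1. State that sensitivity, specificity, kappa and correlation for Aim 1 use only each subject's enrollment pair. This makes the single time point of section 3.1 explicit.
2. State that follow-up pairs form a supportive set, with intervals from a bootstrap that resamples patients and keeps all pairs of a sampled patient together. Report both the number of patients and the number of pairs.

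The bootstrap corrects the interval, not the weighting; reporting both counts lets the reader see how far a few patients dominate. The cost is some wording and a few lines of code, with no new data. The downside is wider intervals for the treated set.
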